The primary objective of the study is to investigate how AGEs accumulation correlates with muscle loss in adult patients with obesity and type 2 diabetes or lipodystrophy with the aim of identifying possible targets to mitigate the metabolomic alterations caused by WD. Specifically, the levels of circulating AGEs in the skin and correlated with the stage of sarcopenia in a group of patients with

SCDU di Endocrinologia

AOU Maggiore della Carità, [name],
[name] [contact]
(Reparto);; [contact]
[contact]

Direttore: [name]

obesity and a T2D diagnosis will be evaluated. In addition, the relationship between disease duration and AGEs levels will be evaluated.

Secondary objective will be to analyze the obtained clinical data to identify metabolites and metabolic pathways responsible for the WD-induced phenotype.

The final aim of the study is therefore to investigate whether high AGE levels correlate with an earlier and/or more pronounced onset of sarcobesity, in conjunction with increased inflammation and oxidative stress.

STUDY DESIGN

Type of study

The present study is cross-sectional observational. The reference population is defined by patients with obesity and a diagnosis of T2D within 15 years of study entry or patients with type 2 diabetes concomitant with lipodystrophic syndrome. This population was chosen as being at high risk for sarcobesity.

Lipodystrophy includes a heterogeneous spectrum of genetic and acquired diseases, characterized by subcutaneous adipose tissue loss, ectopic fat accumulation, insulin resistance, metabolic and cardiovascular diseases, premature aging, sarcobesity and muscle pain, high-grade inflammation, epigenetic dysregulation, and mitochondrial dysfunction. Therefore, patients with T2D and lipodystrophy are found to be highly inflamed, as they generally have a more severe T2D phenotype, presumed to be sarcopenic, and have a high rate of endogenous AGE production. Therefore, patients with lipodystrophy concomitant with T2D will be enrolled as sarcopenic and obese subjects, which represent an excellent strategy for comparison with the diabetic population without lipodystrophy.

SUBJECTS AND METHODS

A total of 195 consecutive subjects afferent to the SCDU of Endocrinology at Eastern Piedmont University between April 2024 and April 2026 who meet the inclusion criteria will be included in the study.

Inclusion criteria:

1. Patients of both sexes
2. Subjects of legal age

SCDU di Endocrinologia

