AOU Maggiore della Carità, [name],
[name] [contact]
(Reparto);; [contact]
[contact]

Direttore: [name]

3. BMI compatible with obesity and diagnosis of type 2 diabetes in good metabolic control (HbA1c < 7.5 %) within 15 years of study entry or diagnosis of lipodystrophy (included in the ECLip - Registry (eclip-web.org))

Exclusion criteria

1. Age under 18 years old
2. Secondary obesity or genetic diseases (Prader Willi syndrome, Down syndrome); metabolic and endocrine (Cushing's syndrome, hypothyroidism);
3. Subjects with: Intestine Bowel disease (IBD), cancer.
4. Established or planned pregnancy during the months of study participation

After reading the study information sheet (see Managing Informed Consent), patients will be enrolled only after signing the informed consent form.

Duration of the study:

The study will last two years corresponding to the enrollment period given the cross-sectional nature of the study.

Definition of sarcobesity indices

According to the ESPEN/EASO consensus statement [26], the following aspects will be considered for the diagnosis of sarcobesity:

1. Skeletal muscle functional parameters defined by muscle strength measured by hand grip strength (Hand grip strength HGS), chair test (seat-lift test five times; 30-second seat test), balance tests, and walking test and walking speed.
2. Body composition by bio-impedance analysis (BIA).

Specifically, the percentage of fat mass (%MG), detected directly by BIA, and the percentage of skeletal muscle mass relative to body mass will be considered for the definition of sarcobesity

Skeletal mass will be calculated as:

$$MS(Kg) = [(h^2/(BIA \text{ resistance}) * 0.401) + (sex * 3.825) + (age * 0.071)] + 5.102$$

Where h indicates height measured in cm, sex is a dichotomous variable that takes value 1 for males and 0 for females, and age is measured in years.

From this measurement, the percentage of skeletal muscle mass (%MMS) will be calculated
$$\%MMS = (MS \text{ (Kg)}) / (\text{Body mass (Kg)}) * 100$$

SCDU di Endocrinologia

AOU Maggiore della Carità, [name],
[name] [contact]
(Reparto);; [contact]
[contact]

Direttore: [name]

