Biochemical evaluation by hematochemical sampling and urine samples as per clinical practice (Blood glucose, complete blood count, HbA1c, AST, ALT, GTT, ALP, CPK, Total cholesterol, HDL cholesterol, Triglycerides, Uric acid, Creatinine, Microalbuminuria, urine test, 25-OH-Vit. D, Calcium, Phosphorus and QPE). Additional parameters of scientific interest will also be evaluated (IL-6, IL-10, IL-17, TNF-alpha, INF-gamma, Leptin and Adiponectin) Samples will be stored at the UPO Biobank (<https://biobank.uniupo.it/en/>). In addition, serum and plasma will be collected for metabolomic analysis, evaluation of cytokine profiles in serum and C-reactive protein, by multiplex assay.

SCDU di Endocrinologia

AOU Maggiore della Carità, [name],
[name] [contact]
(Reparto);; [contact]
[contact]

Direttore: [name]

Analysis

Biochemical parameters according to clinical practice will be analyzed at the clinical biochemistry laboratories of the Maggiore della Carità Hospital in Novara. Metabolomic analyses will be performed at the Center for Translational Research on Autoimmune and Allergic Diseases (CAAD) of the University of Eastern Piedmont. Evaluation of exogenous AGEs will be carried out at the laboratories of the University of Perugia.

Sample size

Given a first-type error α of 0.05 and a power of 80 percent, 195 subjects will be required to observe as significant the correlation between AGEs levels and the indices used to assess the level of sarcobesity of at least 0.2. Given the low prevalence of lipodystrophy and considering a one-year recruitment duration, it is planned to include approximately 35 subjects with lipodystrophy. The remaining 160 subjects will have diabetes and obesity. In addition, considering that the duration of diabetes may affect the levels of AGEs and sarcobesity, both subjects with diabetes for a long time (80 patients) and less than one year (80 patients) will be selected who can be considered comparable to pre-diabetes.

Statistical analysis

Descriptive statistics will be used to summarize the sociodemographic, anthropometric, clinical, and lifestyle-related information collected. Categorical variables will be summarized by absolute frequencies and percentages while numerical variables as mean and standard deviation or median and interquartile range if not normally distributed in accordance with the Shapiro-Wilk test and after observation of QQ-plots.

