Pearson's correlation coefficient or the corresponding nonparametric Spearman's index and confidence intervals will initially be calculated in order to assess the correlation between the level of individual AGEs and MMS, MMSH, body composition parameters, and skeletal muscle functional parameters. Then linear regression models will be used in order to assess the relationship between AGEs and indices defining sarcobesity adjusted for age, sex, duration of diabetes, and other potential confounding factors such as inflammation, western diet adherence, and physical activity levels. The LASSO method will be used for the selection of variables to be included in the multivariable regression models.

Poisson regression models with univariable and multivariable robust variance will be used to estimate prevalence relative risks for the association between AGEs and patient characteristic with the presence of sarcobesity and corresponding confidence intervals.

SCDU di Endocrinologia

AOU Maggiore della Carità, [name],
[name] [contact]
(Reparto);; [contact]
[contact]

Direttore: [name]

An integration of clinical, biochemical data, AGE levels, and patient omics signatures will be performed to develop a multifactorial diagnostic model using multivariate statistical analysis (e.g., factor analysis, principal component analysis, cluster analysis, discriminant analysis, partial principal component analysis, logistic model) and data-driven approaches. Machine learning algorithms will be applied to prioritize and weight risk factors. These analyses will be performed with an in-house statistical consultancy already used by the group.

Expected Results

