With this study, we expect to obtain more information and correlations between nutritional assessment and its impact on inflammation, definition, and progression of sarcopenia, obesity, and T2D, based on body measurements and clinical parameters. Through biochemical, hormonal, and metabolomic analyses performed on the biological samples, we expect to identify possible markers related to the presence of AGEs. In conclusion, the primary expected outcome would be to identify a positive correlation between AGE accumulation in at least one compartment (skin plasma, urine) and the severity of sarcopenia status, so that we can obtain a rapid and noninvasive to identify individuals at high risk of developing MW and identify correlations between AGE levels and other metabolic characteristics, including in lipodystrophic disease.

ETHICAL ASPECTS

The experimental protocol for human studies will be submitted to the Novara Interhospital Ethics Committee, registered on ClinicalTrial.gov before initiation, and conducted in accordance with the Declaration of Helsinki. All enrolled subjects will sign informed consent before participating in the study.

- *Ethical principles for medical research involving human subjects* (Declaration of Helsinki - World Medical Association, current version);
- European Union *Standards of Good Clinical Practice* (ICH/GCP);
- *Convention on Human Rights and Biomedicine* (Oviedo Convention of 04/04/1997);
- Italian codes of ethics for health professions and specific current national regulations on clinical trials.

Management of informed consent

An information sheet explaining the type of study, purpose, procedures, sample and data collection, and possible benefits and risks of the research is available. This information will be presented to interested persons, who will have the freedom to give consent or to be able to withdraw it when the study has already begun.

SCDU di Endocrinologia

AOU Maggiore della Carità, [name],
[name] [contact]
(Reparto);; [contact]
[contact]

Direttore: [name]

Management of sensitive data

The following European and national regulations are kept in mind:

- *Regulation (EU) 2016/679 of the European Parliament and of the Council of April 27, 2016 and subsequent amendments published in the Official Journal of the European Union 127 of May 23, 2018 (GDPR);*

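### Sarcopenia severity is graded only on muscle as a share of body weight, and no planned model names fat mass or BMI, so an AGE association with adiposity could be read as muscle loss

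*Combined protocol and SAP*

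**What the plan says.** **Objective (Study Purpose).** "The primary objective of the study is to investigate how AGEs accumulation correlates with muscle loss in adult patients with obesity and type 2 diabetes". The sentence goes on to include patients with lipodystrophy. The next sentence makes this specific: AGE levels are to be related to the stage of sarcopenia. Under Expected Results, the primary expected outcome is a positive correlation of AGE accumulation with "the severity of sarcopenia status".

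**Index (Definition of sarcobesity indices).** Besides fat percentage (%MG), "the percentage of skeletal muscle mass relative to body mass will be considered for the definition of sarcobesity". Skeletal mass MS in kg is calculated from height, BIA resistance, sex and age, with no term for weight or fat. %MMS is MS divided by body mass, times 100.

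**Cut-offs (same section).** %MMS is impaired below 35.6% in men and 28.4% in women, and severe at or below 28.7% and 23%. Grip strength, chair test and %MG have one cut-off each and no severity grade.

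**Analysis (Statistical analysis).** AGEs are first correlated with MMS, MMSH, body composition and functional measures. MMS and MMSH are not defined, and no index is named as the one that carries the conclusion. Linear models follow, "adjusted for age, sex, duration of diabetes, and other potential confounding factors such as inflammation, western diet adherence, and physical activity levels", with LASSO choosing the variables. Poisson models address the presence of sarcobesity.

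**The concern.** The objective is about muscle. The only graded measure is a ratio with body weight in the denominator, so it worsens when fat increases and muscle does not change. Most of the sample is recruited for obesity, where weight varies widely. If patients with more fat also have higher AGEs, %MMS will correlate with AGEs even when muscle mass does not.

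Nothing planned is certain to separate the two explanations. The initial correlations are unadjusted. The regressions name no measure of adiposity, and LASSO may drop even the covariates that are named. The study could then report that AGE accumulation goes with muscle loss, and propose AGE measurement for identifying people at risk of muscle wasting, when the data show only that it goes with body fat.

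**Working it through.** **The plan's own figure.** The Sample size section gives alpha 0.05, "a power of 80 percent", and "the correlation between AGEs levels and the indices used to assess the level of sarcobesity of at least 0.2". By Fisher's z, two-sided:

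n = ((1.9600 + 0.8416)/atanh 0.2)² + 3 = (2.8016/0.20273)² + 3 = 193.97, so 194.

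The stated 195 is reproduced to within one patient, and power at 195 is 80.2%. Sidedness is not stated; one-sided would give 154. The study is therefore built to detect correlations near 0.2, whatever produces them.

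**Step 1: weight shift at fixed muscle.** Body mass at a cut-off c is MS/(c/100), so the ratio of body mass at the severe cut-off to that at the normal boundary does not depend on MS.

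- Men: 35.6/28.7 = 1.240, a rise of 24.0%.
- Women: 28.4/23 = 1.235, a rise of 23.5%.

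This needs only the plan's cut-offs and constant calculated muscle. As an illustration with assumed heights:

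- A man of 1.75 m on the normal boundary at BMI 30 weighs 30 × 1.75² = 91.9 kg. He reaches severe at 91.9 × 1.240 = 114.0 kg, BMI 37.2.
- A woman of 1.62 m goes from 30 × 1.62² = 78.7 kg to 97.2 kg, BMI 37.0.

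Both ends lie in the obese range.

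**Step 2: how large an induced association could be.** The documents give no AGE–fat correlation, so a range was simulated: 195 patients, 2,000 runs per scenario, AGE depending on fat mass only. Assumed values (men/women): mean fat 36/44 kg, SD 9; mean muscle 32/21.5 kg, SD 4/3; other mass 34/26 kg; half men. Fat is assumed not to alter BIA resistance. The muscle–fat correlation is 0 or 0.4. The table gives results for continuous %MMS adjusted for sex, tested two-sided at 0.05.

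| r(AGE, fat) | r(muscle, fat) | mean r(AGE, %MMS) | false association | with fat mass added |
|---|---|---|---|---|
| 0.2 | 0 | −0.138 | 49% | 5% |
| 0.2 | 0.4 | −0.110 | 33% | 6% |
| 0.3 | 0 | −0.206 | 83% | 4% |
| 0.3 | 0.4 | −0.160 | 61% | 5% |
| 0.4 | 0 | −0.277 | 97% | 5% |
| 0.4 | 0.4 | −0.214 | 85% | 6% |

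With r(AGE, fat) = 0 the rate is 4–5%, as it should be. A hand check of the first two rows: 0.1389 × √192 − 1.960 = −0.036, which gives 49%; 0.1104 × √192 − 1.960 = −0.430, which gives 33%. If %MMS is reduced to normal, impaired and severe, the false rates are 21–36%, 39–69% and 62–90% for the three AGE–fat correlations.

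**Step 3: absolute muscle without fat.** In the same runs, AGE against muscle in kg adjusted for sex alone is significant in 4–5% when muscle and fat are independent. When they correlate at 0.4 it is significant in 18%, 37% and 59%. By construction that association runs towards more muscle with higher AGE. Changing to kilograms is therefore not enough; fat mass has to be in the model.

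**Step 4: the age term.** As printed, MS rises by 0.071 kg per year of age, while the background speaks of age-associated muscle decline. For a man of 1.75 m, 55 years and 450 ohm (assumed), MS is 27.29 + 3.825 + 3.905 + 5.102 = 40.1 kg. With the opposite sign it is 32.3 kg. The ratios in Step 1 are unaffected, but where the cut-offs fall on the weight scale is not: the normal boundary is at 112.7 kg in one case and 90.8 kg in the other.

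**The case against.** The best defence is that the plan does not rest on the severity grade.

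- **No three-level grade is analysed.** Stage and severity appear in the objective and the expected results but are never equated with the %MMS cut-offs. This is fair. However, they are the only severity cut-offs given, and continuous %MMS has the same defect.
- **The diagnosis also needs impaired function.** A reader might infer that a heavy patient with normal muscle and normal function becomes a sarcobesity case, so that the primary result could be met by fat alone. The documents do not support that: impaired grip or chair test is listed together with %MG and %MMS. The protection is partial, because among patients with impaired function extra fat can still carry someone over the %MMS limit.
- **Other indices are already planned.** AGEs will be correlated with function, MMS and MMSH, so it would be wrong to say that the plan looks only at %MMS. What is missing is a statement of which index supports a muscle-loss claim.
- **The confounder list is open.** It is illustrative, and weight, BMI and BIA composition are collected. Nothing excludes fat mass, but nothing secures it.
- **An AGE–fat link is not established.** The background places AGEs in Western-diet foods and says that fructose-derived AGEs activate lipogenesis. It does not say that the diet raises fat mass, and it gives no correlation. The link is plausible but unquantified. The lipogenesis statement also means that fat could lie downstream of AGEs, so adjusting for it is not automatically neutral.
- **Not everyone is recruited for obesity.** About 35 of 195 enter through lipodystrophy, with subcutaneous fat loss and high endogenous AGE production. Lower fat raises %MMS at given muscle, which could partly offset the effect in the pooled sample. The simulation does not model this group.

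Weight-relative muscle is also a reasonable part of defining sarcobesity, which the protocol attributes to a consensus statement. The difficulty lies only in the inference to muscle loss.

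**Conclusion.** The point holds in a limited form. %MMS mixes muscle with adiposity: at constant calculated muscle, a 24.0% (men) or 23.5% (women) rise in weight spans the distance from normal boundary to severe. That much follows from the plan's own cut-offs. Because the objective speaks of muscle loss and no named adjuster captures fat, an AGE–%MMS association could arise without any muscle effect.

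How often is conditional. For an AGE–fat correlation between 0.2 and 0.4, the false-association rate is roughly 33% to 97%, falling to 4–6% with fat mass in the model. These rates rest on the assumed body-composition values, on unchanged BIA resistance and on AGE acting through fat only. They are not a prediction for this study, and a real %MMS association could still include true muscle loss. The sarcobesity diagnosis and the planned functional correlations are less exposed. The matter should be settled before analysis; it does not invalidate the design.

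**What to change.** 1. First check the sign of the age term in the MS equation, since any analysis of MS in kg depends on it.
2. Keep %MMS and %MG for classifying sarcobesity.
3. In Statistical analysis, define MMS and MMSH. Add one prespecified regression of MS (kg) on AGEs with height, BIA fat mass, age and sex forced in rather than left to LASSO. Report it with and without fat mass, because fat may lie downstream of AGEs.
4. In Expected Results, state that muscle loss will be concluded from this model and hand grip strength. An association seen only on %MMS is to be reported as relative muscle deficit.

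The claim should not be made conditional on MMSH pointing the same way. MMSH is undefined, and with the printed equation an age effect could push it upward together with AGEs and mask a true deficit.

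The cost is some wording and one extra model on data already collected. The downsides are a possibly weaker claim and possible over-adjustment, which the paired reporting in item 3 makes visible.

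### The powered correlation pools recruitment strata that the plan expects may differ on AGEs and muscle status, and no analysis secures adjustment for lipodystrophy status

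*Combined protocol and SAP*

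**What the plan says.** The Sample size section powers a single correlation: "195 subjects will be required to observe as significant the correlation between AGEs levels and the indices used to assess the level of sarcobesity", with a target of at least 0.2, alpha 0.05 and 80% power. It then fills that total: "it is planned to include approximately 35 subjects with lipodystrophy", and "The remaining 160 subjects will have diabetes and obesity". The 160 are split into 80 with long-standing diabetes and 80 with less than one year, because duration may influence both AGE levels and sarcobesity.

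Under Study design, Type of study, lipodystrophy patients with T2D are "presumed to be sarcopenic, and have a high rate of endogenous AGE production". The same section gives their role: "patients with lipodystrophy concomitant with T2D will be enrolled as sarcopenic and obese subjects, which represent an excellent strategy for comparison" with diabetic patients who do not have lipodystrophy.

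The Statistical analysis section begins with Pearson or Spearman correlations, without adjustment or stratification. Linear regressions follow, adjusted for age, sex, diabetes duration and an open list of further confounders (inflammation, diet and physical activity are its examples). LASSO selects the variables and none is declared fixed. Univariable and multivariable Poisson models address the presence of sarcobesity. Lipodystrophy status is not named as a covariate, stratum, subgroup or interaction in any of them.

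The Study purpose section states the population in two ways. The general primary objective concerns "muscle loss in adult patients with obesity and type 2 diabetes or lipodystrophy". The sentence that makes it specific says AGE levels "correlated with the stage of sarcopenia in a group of patients with" "obesity and a T2D diagnosis will be evaluated", which leaves out lipodystrophy.

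**The concern.** When groups with different means on two variables are pooled, the overall correlation mixes the relation inside the groups with the contrast between them. The plan itself gives reason to expect such a contrast twice: between lipodystrophy and the rest, and between long and short diabetes duration.

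Expected Results names a positive correlation between AGE accumulation and sarcopenia severity as the primary expected outcome. If lipodystrophy patients have higher AGEs and worse muscle status, that result could appear with no AGE-muscle relation within any stratum. It would largely restate what the design section already presumes about these patients. The lipodystrophy group is enrolled for comparison, but no listed analysis makes that comparison or separates it from the main correlation.

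**Working it through.** **1. Reproduce the plan's figure.** Inputs from Sample size: r = 0.2, alpha 0.05, power 80%. Sidedness is not stated; two-sided is assumed because it reproduces the number (one-sided gives 154).

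n = ((1.960 + 0.842) / atanh(0.2))² + 3, with atanh(0.2) = 0.2027, gives 193.97, so 194 against the stated 195. Power at 195 is 80.2%. The sample size is right for one homogeneous correlation.

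**2. Effect of pooling lipodystrophy with the rest.** Share p = 35/195 = 0.179, so p(1−p) = 0.147. With within-group SD 1, within-group correlation w, and mean shifts dx and dy:

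pooled r = (w + 0.147·dx·dy) / √[(1 + 0.147·dx²)(1 + 0.147·dy²)]

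Set w = 0 and equal shifts d towards higher AGEs and worse muscle status. The formula reduces to 0.147d² / (1 + 0.147d²). The shifts are assumptions.

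| Assumed d (SD) | Pooled \|r\| | Rejection at n = 195, unadjusted |
|---|---|---|
| 0.5 | 0.04 | 8% |
| 0.75 | 0.08 | 19% |
| 1.0 | 0.13 | 43% |

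In simulation (20,000 replicates, bivariate normal, 35 + 160), the unadjusted test rejects 7.8%, 18.8% and 43.8%. A lipodystrophy-adjusted test rejects 5.0–5.2%, provided that the 160 are homogeneous.

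**3. The 160 may not be homogeneous.** The 80/80 duration split acts in the same way and is balanced, so p(1−p) = 0.25. Simulate 35 + 80 + 80 with zero within-stratum correlation and assumed duration shifts of 0.5, 0.75 and 1.0 SD on both variables:

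- adjusted for lipodystrophy only, all 195: about 10–11%, 30% and 67% rejection;
- unadjusted, within the 160: about 11–12%, 34–35% and 73%;
- adjusted for both lipodystrophy and duration stratum: back to about 5%.

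Lipodystrophy adjustment alone is therefore not a sufficient remedy.

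**4. Power after adjustment.** For a partial correlation with k terms, replace n − 3 by n − 3 − k, at r = 0.2.

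| Analysis | n | k | Power |
|---|---|---|---|
| Unadjusted | 195 | 0 | 80.2% |
| Adjusted for the three strata | 195 | 2 | 79.8% |
| Obese-T2D, unadjusted | 160 | 0 | 71.9% |
| Obese-T2D, adjusted for duration stratum | 160 | 1 | 71.6% |
| Lipodystrophy alone | 35 | 0 | 20.9% |

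The second row, for example: 0.2027 × √190 = 2.794, and Φ(2.794 − 1.960) = 79.8%. These figures hold for Pearson-type correlations.

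**The case against.** The strongest reply has four parts.

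- **The correlations are described as a first step, and adjusted models follow.** True. Those models name duration and inflammation, and the design section calls lipodystrophy patients highly inflamed, so part of the contrast may already be adjusted away. The open confounder list would also allow lipodystrophy status to be added. But permission is not pre-specification, LASSO could drop any of these terms, and the analysis that carries the power statement is the unadjusted correlation.
- **A marginal association is a legitimate target.** The plan wants a marker of high-risk individuals and recruits a wide range on purpose. This stands as a reason to keep the unadjusted correlation as a descriptive result. It does not answer whether AGEs relate to muscle loss within comparable patients.
- **The expected group difference is narrower than all AGE measures.** A reader might infer that the plan predicts a lipodystrophy contrast on every AGE measure. It does so only for endogenous AGEs, while the study purpose concerns diet-derived AGEs. So the lipodystrophy part of the concern is most plausible for the endogenous measures.
- **The population is not generally in conflict.** Sample size, the general objective and the inclusion criteria all admit both groups. A reader might also count Expected Results as a conflict because it mentions lipodystrophic disease. That phrase attaches to correlations with other metabolic characteristics and agrees with enrolling both groups. Only the specific-objective sentence is narrower.

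**Conclusion.** The point holds and should be fixed. The powered correlation pools strata that the plan expects, or allows, to differ on both variables. Lipodystrophy status is named in no analysis, and adjustment for duration is named but not secured against LASSO.

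How large the distortion would be cannot be determined, because the documents give no stratum means or SDs. The rejection rates of 8%, 19% and 43%, and the duration figures, are illustrations under assumed same-direction shifts and normal data. They are not properties of this plan. Confidence is high on the omission and on the mismatch in the objective sentence, not on the size of the bias.

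Two stronger readings are not supported. A reader might infer that 195 is miscalculated; it reproduces. A reader might infer that adjusted power falls to some definite lower figure. That would require 0.2 to have been meant as the pooled value and would also require the stratum shifts, and the documents supply neither.

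**What to change.** 1. State that the powered population is all 195, and align the specific-objective sentence in Study purpose with it.
2. Make the powered analysis the partial correlation (partial Spearman where Spearman is used), or the regression coefficient, adjusted for recruitment stratum: lipodystrophy, long-duration T2D, T2D under one year. Restate 0.2 as the stratum-adjusted correlation, with 79.8% power at 195. Keep the unadjusted correlation as descriptive.
3. Force the stratum terms into the multivariable linear and Poisson AGE models, outside LASSO. The univariable Poisson models stay unadjusted.
4. Also report the correlation in the 160 obese-T2D patients, adjusted for duration stratum (71.6% power at r = 0.2). Label results in the 35 alone (about 21% power) as exploratory.
5. Reconcile Type of study, which describes lipodystrophy patients as having T2D, with inclusion criterion 3, which as worded does not require it. Duration of diabetes is undefined for a non-diabetic patient. Any model restricted to T2D patients could have fewer than 195 subjects, and the powers above would not apply to it.

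**Cost.** Wording, and no extra patients to add the terms. The date of diabetes diagnosis is already collected. Lipodystrophy status follows from the entry criterion, although the list of data to be collected does not name it, so a database field should be confirmed. The real cost is interpretive: 0.2 must be read as a within-stratum correlation. If it was meant as the pooled value and the strata differ in the same direction on both variables, power for the adjusted analysis would be lower, by an amount the documents do not allow to be computed.

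### The primary expected outcome is met by a positive AGE correlation in any one compartment, but alpha 0.05 and N=195 fit a single correlation, and no primary AGE-index pair or multiplicity rule is fixed.

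*Combined protocol and SAP*

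**What the plan says.** - **Expected Results.** The primary expected outcome is a "positive correlation between AGE accumulation in at least one compartment (skin plasma, urine) and the severity of sarcopenia status". The protocol links it to a quick, non-invasive way of picking out people likely to lose muscle.
- **Sample size.** "Given a first-type error α of 0.05 and a power of 80 percent, 195 subjects will be required" to show as significant "the correlation between AGEs levels and the indices used to assess the level of sarcobesity of at least 0.2". One alpha and one effect size are given, while the indices are plural.
- **Statistical analysis.** "Pearson's correlation coefficient or the corresponding nonparametric Spearman's index and confidence intervals will initially be calculated", covering the "correlation between the level of individual AGEs and MMS, MMSH, body composition parameters, and skeletal muscle functional parameters". Adjusted linear models with LASSO selection and Poisson models follow. The section gives no significance level, testing order or alpha split, and does not say which result decides the primary outcome.
- **Study Purpose.** The text nearest to a primary pair follows the primary objective. It speaks of AGEs that are both circulating and in the skin, related to sarcopenia stage. It does not settle which compartment is meant or how stage is scored for a correlation.
- **Quantification of AGEs.** Skin fluorescence is described, together with more than one blood measure: free plasma AGEs (ELISA, fluorescence assay) and haemoglobin-bound AGEs (HbA1c). No urine AGE assay is described. The urine samples listed later are for routine clinical tests.

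**The concern.** An outcome met by any one of several correlations has a larger chance of being met by luck than one correlation tested alone. The plan provides for one correlation, yet leaves open the compartment, the assay within blood, the index, the coefficient and the model. All of these could be settled after the data are seen and the primary outcome still reported as achieved. The error rate attached to that claim would then not be the stated 0.05 and could not be worked out from the plan. This matters because the claim is meant to support a screening use.

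**Working it through.** **Inputs from the protocol.** Alpha 0.05, power 80%, r = 0.2 and N = 195 (Sample size); at least one compartment, positive direction (Expected Results); several indices (Statistical analysis).

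**Assumptions.** Each AGE measure is tested at two-sided 0.05. All true correlations are zero when error rates are computed. AGE measures correlate 0 to 0.7 with one another. The documents give none of these.

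**1. The plan's own figure.** With Fisher's z,

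N = [(z₀.₉₇₅ + z₀.₈₀) / atanh(r)]² + 3 = [(1.960 + 0.842) / 0.2027]² + 3 = 193.97, so 194.

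Power at 195 = Φ(0.2027 × √192 − 1.960) = Φ(0.849) = 80.2%.

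A one-sided test would need 154. The stated 195 therefore fits a single two-sided Pearson correlation, with no allowance for further tests.

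**2. False-claim rate against one index, k AGE measures.** For independent measures the rate is 1 − (1 − 0.025)^k in the positive direction and 1 − (1 − 0.05)^k in either direction. With k = 2: 1 − 0.975² = 4.94% and 1 − 0.95² = 9.75%. With k = 3: 1 − 0.975³ = 7.31% and 1 − 0.95³ = 14.26%.

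For AGE measures with common correlation ρ, the test statistics are taken as equicorrelated normal. The positive-direction rate is 1 − ∫ φ(u) Φ[(1.96 − √ρ·u)/√(1 − ρ)]^k du. The two-direction rate has the same form, using the probability of lying between −1.96 and 1.96.

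| k | ρ | Positive only | Either direction |
|---|---|---|---|
| 1 | – | 2.50% | 5.00% |
| 2 | 0 | 4.94% | 9.75% |
| 2 | 0.3 | 4.76% | 9.51% |
| 2 | 0.7 | 4.17% | 8.35% |
| 3 | 0 | 7.31% | 14.26% |
| 3 | 0.3 | 6.83% | 13.62% |
| 3 | 0.7 | 5.46% | 10.92% |

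In the positive direction, relative to one test, this is 4.17/2.5 = 1.7 to 4.94/2.5 = 2.0 times for two measures, and 5.46/2.5 = 2.2 to 7.31/2.5 = 2.9 times for three. Simulated raw data (60,000 datasets of 195, Pearson t-test) agree: 4.1-5.1% and 8.3-9.8% for two measures, 5.5-7.3% and 11.0-14.4% for three.

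**3. If several indices may count.** Take 2 AGE measures × 4 indices = 8 pairs, an assumed count. If independent: 1 − 0.975⁸ = 18% positive only and 1 − 0.95⁸ = 34% in either direction. With correlation 0.7 among AGE measures and among indices, simulation gives about 10% and 21%.

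**4. What adjustment would cost.** Bonferroni, the first step of Holm, has detectable r = tanh[(z + 0.842)/√192] at 80% power.

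- Two measures (alpha 0.025, z = 2.241): r = 0.219; power at r = 0.2 is 71.5%.
- Three measures (alpha 0.0167, z = 2.394): r = 0.229; power at r = 0.2 is 66.1%.

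Holm's power per test is at least this high.

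**The case against.** The sentence stands under Expected Results and reads as a hope, not a test procedure. The study is cross-sectional and observational, its purpose is described as exploring, and the analysis section plans coefficients with confidence intervals. On this view, strict error control is a matter of preference. In addition, Study Purpose may already point to skin AGEs and sarcopenia stage. Finally, with only skin and plasma, one index and positive results only, the rate is below the 0.05 in the plan.

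Much of this stands. There is no formal decision rule, and 0.05 per measure is an assumption. The mildest case does stay under 5%. An explicit exploratory label would largely meet the point.

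It does not remove the point. The protocol calls the outcome primary, sets a type I error and sizes the study on significance, and it nowhere labels these correlations exploratory. The Study Purpose wording is unclear and Expected Results widens it to any compartment. The mildest case also needs one index and one blood measure to be fixed, and the plan fixes neither.

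A reader might infer that the false-claim rate is two to three times nominal in every case, or always above 5%. The figures do not support that: two measures against one index never quite reach a doubling, and three compartments require a urine AGE measure that the protocol does not describe.

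**Conclusion.** The point holds as a gap in specification with a modest to moderate effect on error. For one index, the positive-direction false-claim rate is about 1.7-2.0 times that of one test with two AGE measures and 2.2-2.9 times with three. It is larger if several indices or blood assays may count. By how much cannot be fixed from the documents, and the 2 × 4 case is only an illustration. All rates rest on two-sided 0.05 per test, no true correlation, and AGE measures correlated 0 to 0.7.

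A reader might also infer that 195 subjects are too few. That does not follow: without adjustment, the chance of at least one significant result at r = 0.2 is 81% or more, even if only one of two or three AGE measures is associated. The fault is an undefined error rate for the primary claim. The data remain usable, and the plan should be amended before analysis.

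**What to change.** Before analysis, name one primary AGE measure and one primary sarcopenia index, tested at two-sided 0.05, and state the expected sign (for percentage skeletal muscle mass, more severe sarcopenia means a negative correlation). N=195 and 80.2% power at r = 0.2 are kept for Pearson with complete data. Report all other pairs as secondary or exploratory with Holm or FDR adjustment.

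Alternatively, keep the at-least-one rule against one named index, apply Holm across the AGE measures actually tested, and restate the detectable correlation per test as about 0.22 (two measures) or 0.23 (three).

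In either case, reconcile Study Purpose, Quantification of AGEs and Expected Results on which compartments are measured, including urine. The choice is the sponsor's.

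The cost is protocol wording, with no added subjects or assays. The downside is that associations outside the primary pair become secondary, or that the stated detectable correlation rises slightly from 0.20.
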